Objectives: To test the comparative effectiveness of a conjoint analysis intervention compared to usual care and identify preferred attributes of alternative prostate cancer treatments (including active surveillance) that will aid in designing ways to help patients weigh treatment attributes. We employ values markers, to represent clusters of values for particular aspects of treatments that are valued most by individual patients. Study hypothesis is that conjoint task may have an effect on treatment choice and prostate cancer patients whose treatment is more concordant with their values markers will have improved outcomes. **Study Design:** We propose a two phase study design. In Phase 1, to identify the attributes, we will conduct six focus groups of prostate cancer patients and two focus groups with physicians who treat prostate cancer. Next, we will develop a conjoint task instrument using the attributes identified in focus groups and pilot test it. This task requires the patients to trade-off various treatments by assessing relative importance of particular treatment attributes. Results of Phase 1 will yield a conjoint analysis instrument to identify profiles of treatment values markers, and will be used in Phase 2 to determine common values markers, or profiles of treatment attributes prostate cancer patients value most. Phase 2 consists of a stratified (UPHS, Fox Chase, and PVAMC) randomized controlled trial study of men with localized prostate cancer, aged 45 and randomized to either the conjoint task intervention group or usual care control group, and followed for up to 24 months for objective and subjective outcomes.

Objectives

Overall objectives

Objectives: To test the comparative effectiveness of a conjoint analysis intervention compared to usual care and identify preferred attributes of alternative prostate cancer treatments (including active surveillance) that will aid in designing ways to help patients weigh treatment attributes.

Primary outcome variable(s)

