
phase is critical for determining the salient characteristics of a product or service. Typically, researchers use focus groups that consist of end-users or "experts", to learn from people who have the most experience with the service, but researchers also convene focus groups of people who have little or no experience with a service to learn what may be important for a new user. Focus groups typically are comprised of 6 to 10 participants who do not know one another and who have similar associations to the topic being investigated (i.e., newly diagnosed localized PCa patients). We will make an effort to recruit equal number of surgical and radiation treatment patients and men younger than age 65 and age 65. It is recommended that one conduct at least two focus groups to capture experiences from similar groups of individuals [254-256]. Drs. [name], [name], and [name] each have extensive experience in racial and ethnic disparity research and will carefully construct each focus group. Thus, we will conduct focus groups with good representation from minority and non-minority patients. Of the six patient focus groups, three will be with newly diagnosed patients yet to make treatment decision; and three will be with those who underwent treatment one year ago, providing additional insight into what they wish they had known about the less immediate outcomes and aspects of treatment. In contrast to individual interview, focus group participants relate their experiences and reactions among peers with whom they likely share some common frame of reference. The discussions stimulated in a group setting and listening to others' experiences has the potential to stimulate memories, ideas and experiences relevant to the topic at hand [254-256]. Overarching goal of focus groups is to obtain perspectives of two of the key stakeholders (patients and physicians) about those components or features of PCa care are important to consider in choosing a treatment. The most commonly mentioned and strongly weighted features of treatment across the focus groups will be used to create the conjoint task (to be used in Phase2). If saturation of emerging themes is not reached after six focus groups, we will conduct additional focus groups until saturation occurs. (See Appendix for interview guide that was developed using results of our prior focus group of physicians, discussed in preliminary work). (3) Assigning levels to the attributes. Levels of an attribute may be cardinal (e.g. waiting time, missed work), ordinal (e.g. level of pain) or categorical (e.g. surgery or radiation treatment). Attribute levels will be identified and aligned with the active surveillance (AS) and five active treatment options being studied (RP, RALP, BT, EBRT, PT), reviewed for appropriateness and wording by the study investigators and advisory board members. (4) Developing choice scenarios. Scenarios will describe services, treatment options and outcome configurations for the attributes and level chosen. We will use a fractional factorial design to reduce the number of paired comparisons to the smallest number necessary for efficient estimation of utility weights [49,183,188]. (5) Conjoint task instrument testing. We will pilot test the conjoint task instrument for appropriateness of attributes, levels, language and ease of administration in 20 PCa patients. PHASE 2 Study Population: We will use stratified randomized control trial to study association between value markers and objective (complications and cancer recurrence) and subjective (HRQoL, psychological wellbeing) outcomes across intervention groups, over 24 month period. We will recruit newly diagnosed localized PCa patients from UPHS (Hospital of University of Pennsylvania, Presbyterian Medical Center, and Pennsylvania Hospital), Fox Chase Cancer Center and Philadelphia Veterans Administration Medical Center (PVAMC) and randomize them to conjoint analysis intervention (n=360) or control group (n=360). D.2.1.1 Participants: The sample will consist of 720 newly-diagnosed PCa patients. Inclusion criteria are: (1) treated for PCa at UPHS, Fox Chase Cancer Center or PVAMC; (2) aged 45 years; (3) newly diagnosed with localized PCa and TNM stage T3a; (4) community dwelling; (5) Gleason score 8; (6) low (PSA 10 ng/ml, Gleason 6, clinical stage T1-2a), intermediate (PSA 10 -20 ng/ml, Gleason 7, clinical stage T2b), and high risk (PSA 20, Gleason 8, clinical stage T2c-3a) group [45] and (7) provide informed consent. Exclusion criteria are: (1) Distant, metastatic or un-staged PCa at diagnosis; (2) visited the clinics to obtain second opinion only; (3) moved to another location; (4) unable to communicate in English and (5) cognitive impairment (Mini Mental State Exam or MMSE score < 21). MMSE is a standardized mental status examination widely used for clinical and research purposes [197,198]. D.2.1.2 Recruitment and participant availability: Participants will be recruited from UPHS, PVAMC and Fox Chase Cancer Center's urology and radiation oncology clinics using recruitment protocols that we have successfully used in our prior and ongoing PCa studies. Recruitment will occur in seven steps: 1) determining potential eligibility; 2) obtaining consent from patients urologist/physician; 3) confirming eligibility; 4) screening via phone and interview to assess willingness to participate; 5) obtaining informed consent and HIPAA permissions; 6) baseline assessments; and 7) follow-up assessments. The study and consent form comply with HIPAA Standards for Privacy of Individually Identifiable Health Information. The draft study design and protocol have been approved by the University of Pennsylvania IRB. Future changes will be reviewed and approved prior to implementation. Participant availability: UPHS is a large hospital and physician network in greater Philadelphia area. Approximately 1,600 patients with newly diagnosed PCa are evaluated annually: 40-50% undergo surgery (RP or RALP); 30-40% undergo EBRT

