
or BT; 10-20% undergo PT. The urology clinic at PRINCIPAL INVESTIGATOR (LAST, FIRST, MIDDLE): [name] PCORI Research Plan: Research Strategy 9 the Hospital of the University of Pennsylvania (HUP) treats more than 60% of this group; the rest are treated at Presbyterian Medical Center and Pennsylvania Hospital. Additionally, UPHS has a proton therapy center, providing a unique opportunity to study this new technology. The Philadelphia Veterans Administration Medical Center (PVAMC) cares for 33,000 veterans in Philadelphia area and evaluates ~400 patients with newly diagnosed PCa each year. Fox Chase Cancer Center evaluates ~500 patients with newly diagnosed PCa each year. Together, UPHS, PVAMC, and Fox Chase Cancer Center provide care to socio-demographically diverse population of ~2,500 men newly diagnosed with PCa each year. Thus, our study sample requirement of 720 patients (33% of the available pool) can be fulfilled comfortably, as demonstrated by the successful recruitment for our earlier studies. Recruitment: Prior to study initiation, investigators will explain the study objectives to physicians who actively treat PCa at the UPHS, PVAMC, Fox Chase urology clinics. During a patient's initial visit, Drs. [name], [name], or [name] will briefly introduce the study to the patient. Each week, the research assistant will contact the participating physician offices to obtain contact information for those patients who have expressed an interest in the study. Potential participants will be contacted during their office visits, at which time those eligible may agree to participate and provide informed consent, request additional information and/or time to think or request to be contacted later. Patients who request to be contacted later will be sent study information, a consent form and a prepaid return envelope. Participants will discuss the consent form with research assistant prior to signing, at which time all questions will be answered. During enrollment, compensation of \$20 will be provided. Using a similar recruitment strategy in our prior PCa studies, we had achieved enrollment and retention rates of 85% or higher. The expected number of 60 participants in each treatment group (AS, RP, RALP, EBRT, BT or PT) will be achieved as follows: (1) each recruited participant randomly assigned to the conjoint analysis intervention group will meet with research assistant to complete the computer-based conjoint analysis tasks and other surveys before initiation of treatment or making a treatment decision; (2) after treatment decision is made, patients (both cases and controls) will be assigned to the appropriate group based on treatment; (3) this process will continue until we reach the required number of participants in each group. To achieve this, we may evaluate and obtain baseline data including conjoint tasks from patients in excess of the required 360 participant each in the intervention and control groups. Based on our prior prospective cohort studies, to fulfill sample requirement of 60 participant in each treatment group ($60 \times 2 \times 6 = 720$), allowing for attrition we expect to obtain baseline assessment including conjoint tasks for 800 participants (10% excess). The cohort that does not get assigned for further follow-up due to targeted group enrollment accrual will be analyzed to ensure comparability. D.2.2 Process of stratified randomization: We will recruit 720 participants stratified by three hospitals-UPHS, PVAMC, or Fox Chase Cancer Center (Figure 3). [name] will create randomization sequences for each hospital using a pseudo-random number generator with random blocking and will place the treatment assignments in sealed, opaque envelopes. All investigators, staff and referring physicians will be masked to the treatment assignment, except the research assistant who will open the envelope and notify participants of group assignment. Participants will be instructed not to reveal their group status to physicians or study personnel, except in case of emergency or if necessary for medical reason, which we believe to be unlikely. D.2.2.1 Conjoint analysis intervention The primary goal of patient-centered PCa care is to engage patients and their families in meaningful and thorough interactions with their healthcare providers to develop accurate and well-conceived treatment choice, using all available medical information appropriately, while also considering the medical, social and cultural needs and desires of the patient and family. It is important for providers to solicit patient preferences and not make assumptions about which treatment and associated side effects patients are more likely to prefer or feel is best for them. Results of conjoint analysis will be shared with the participants of the intervention group, family members, and treating physicians prior to treatment decision. D.2.2.2 Usual care controls: Participants from this group will receive usual care that consists of standard educational material about various treatment options. D.2.3 Data collection and follow-up: After obtaining informed consent, baseline data will be obtained in person prior to the initiation of treatment. Participants will meet with the research assistant to complete the PRINCIPAL INVESTIGATOR (LAST, FIRST, MIDDLE): [name] PCORI Research Plan: Research Strategy 10 computer-based conjoint analysis tasks. Patient identifiers will be removed to maintain data confidentiality. Only the PI will have access to the master files. For conjoint analysis, each participant will be asked to express his preference for attributes and attribute levels for active surveillance and five active treatments for clinically localized PCa (RP, RALP, EBRT, PT, BT) based on choice sets presented. The choices will vary based on the differing attributes of various treatments ascertained in prior work and focus groups. After pilot testing and refining the conjoint task in Phase 1, final attributes and levels will be used. Trade-offs

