obtaining consent from patients urologist/physician; 3) confirming eligibility; 4) screening via phone and interview to assess willingness to participate; 5) obtaining informed consent and HIPAA permissions; 6) baseline assessments; and 7) follow-up assessments. The study and consent form comply with HIPAA Standards for Privacy of Individually Identifiable Health Information. The draft study design and protocol have been approved by the University of Pennsylvania IRB. Future changes will be reviewed and approved prior to implementation. Participant availability: UPHS is a large hospital and physician network in greater Philadelphia area. Approximately 1,600 patients with newly diagnosed PCa are evaluated annually: 40-50% undergo surgery (RP or RALP); 30-40% undergo EBRT or BT; 10-20% undergo PT. The urology clinic at the Hospital of the University of Pennsylvania (HUP) treats more than 60% of this group; the rest are treated at Presbyterian Medical Center and Pennsylvania Hospital. Additionally, UPHS has a proton therapy center, providing a unique opportunity to study this new technology. The Philadelphia Veterans Administration Medical Center (PVAMC) cares for 33,000 veterans in Philadelphia area and evaluates ~400 patients with newly diagnosed PCa each year. Fox Chase Cancer Center evaluates ~500 patients with newly diagnosed PCa each year. Together, UPHS, PVAMC, and Fox Chase Cancer Center provide care to socio-demographically diverse population of ~2,500 men newly diagnosed with PCa each year. Thus, our study sample requirement of 720 patients (33% of the available pool) can be fulfilled comfortably, as demonstrated by the successful recruitment for our earlier studies. Recruitment: Prior to study initiation, investigators will explain the study objectives to physicians who actively treat PCa at the UPHS, PVAMC, Fox Chase urology clinics. During a patient's initial visit, Drs. [name], [name], or [name] will briefly introduce the study to the patient. Each week, the research assistant will contact the participating physician offices to obtain contact information for those patients who have expressed an interest in the study. Potential participants will be contacted during their office visits, at which time those eligible may agree to participate and provide informed consent, request additional information and/or time to think or request to be contacted later. Patients who request to be contacted later will be sent study information, a consent form and a prepaid return envelope. Participants will discuss the consent form with research assistant prior to signing, at which time all questions will be answered. During enrollment, compensation of \$20 will be provided. Using a similar recruitment strategy in our prior PCa studies, we had achieved enrollment and retention rates of 85% or higher. The expected number of 60 participants in each treatment group (AS, RP, RALP, EBRT, BT or PT) will be achieved as follows: (1) each recruited participant randomly assigned to the conjoint analysis intervention group will meet with research assistant to complete the computer-based conjoint analysis tasks and other surveys before initiation of treatment or making a treatment decision; (2) after treatment decision is made, patients (both cases and controls) will be assigned to the appropriate group based on treatment; (3) this process will continue until we reach the required number of participants in each group. To achieve this, we may evaluate and obtain baseline data including conjoint tasks from patients in excess of the required 360 participant each in the intervention and control groups. Based on our prior prospective cohort studies, to fulfill sample requirement of 60 participant in each treatment group ($60 \times 2 \times 6 = 720$), allowing for attrition we expect to obtain baseline assessment including conjoint tasks for 800 participants (10% excess). The cohort that doesn't get assigned for further follow-up due to targeted group enrollment accrual will be analyzed to ensure comparability. D.2.2 Process of stratified randomization: We will recruit 720 participants stratified by three hospitals-UPHS, PVAMC, or Fox Chase Cancer Center (Figure 3). [name] will create randomization sequences for each hospital using a pseudo-random number generator with random blocking and will place the treatment assignments in sealed, opaque envelopes. All investigators, staff and referring physicians will be masked to the treatment assignment, except the research assistant who will open the envelope and notify participants of group assignment. Participants will be instructed not to reveal their group status to physicians or study personnel, except in case of emergency or if necessary for medical reason, which we believe to be unlikely.

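### Treatment-cell quotas leave randomised men unfollowed, which contradicts the Aim 3 intent-to-treat analysis and biases the arm comparison if the intervention shifts treatment choice

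*Combined protocol and SAP*

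**What the plan says.** The order of events is in Study Design, D.2.1.2, and is repeated under Subject recruitment. A man is assigned to an arm before he decides on treatment. Then "after treatment decision is made, patients (both cases and controls) will be assigned to the appropriate group based on treatment", and "this process will continue until we reach the required number of participants in each group". The target is 60 men for each of six treatments in each arm (60 x 2 x 6 = 720). To reach it, the team may take baseline data from "patients in excess of the required 360 participant each in the intervention and control groups", and it expects about 800 men with baseline data. Of those beyond the targets it says: "The cohort that does not get assigned for further follow-up due to targeted group enrollment accrual will be analyzed to ensure comparability".

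Other sections say something different:

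- **Analysis Plan, Specific Aim 3:** the analysis is intent-to-treat and includes every randomised man, even those who leave the study.
- **D.2.3, Study duration and Procedures:** all participants complete surveys at 3, 6, 12 and 24 months.
- **Phase 2 Study Population, Study duration and Target population:** 360 men are randomised to each arm. The Accrual section's power calculation also assumes 720 men eligible for randomisation.
- **Abstract:** the hypothesis is that the "conjoint task may have an effect on treatment choice". Aim 3 makes choice an outcome, namely active surveillance (AS) rather than active treatment in low-risk men.

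**The concern.** The quota variable is measured after randomisation and is the thing the intervention is meant to move. If more intervention men choose AS, that cell fills sooner in the intervention arm and more of its AS choosers go unfollowed. The followed men in the two arms are then different selections, and randomisation no longer protects the comparison of HRQoL (named as primary in the Accrual section), regret and satisfaction.

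The planned safeguards do not reach this:

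- A comparability check on the unfollowed men cannot supply survey outcomes that were never collected.
- The propensity-score and instrumental-variable methods address treatment received within each arm, not selection between arms.
- Aim 3 also stratifies by treatment type without saying that arm contrasts within a treatment are not randomised.

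The number randomised is unclear too. It is 720 in some places, while D.2.1.2 allows more than 360 per arm. The 10% loss allowance appears both inside the 720 (Accrual) and between 720 and 800 (D.2.1.2).

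**Working it through.** **1. The plan's own figures reproduce.** 60 x 2 x 6 = 720, and 720/0.9 = 800. The detectable difference for the mean of four follow-ups is (1.96 + 0.842) x sqrt[2 x SD² x (1 + 3 x 0.3)/4 / n]. It uses the Accrual section's intra-class correlation of 0.3, 80% power and two-sided 0.05. After 10% loss:

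| | n per arm | SD 8 | SD 14 |
|---|---|---|---|
| 360 randomised per arm | 324 | 1.21 | 2.12 |
| 400 randomised per arm | 360 | 1.15 | 2.02 |
| 60 per cell | 54 | 2.97 | 5.20 |

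The stated 1.2 and 3.0 points correspond to SD 8.

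**2. Illustrative inputs (assumptions, not in the documents).** 400 men are randomised per arm and the first 60 in each cell are kept. Low-risk men are 30%, 50% or 70% of the sample, and only they choose AS. AS rates in low-risk men are 20% v 35% or 30% v 45%, a true difference of 15 points. Active treatments split equally, or in proportion to the midpoints of the UPHS ranges.

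**3. One case by hand** (70% low-risk, 30% v 45%, equal split, expected counts).

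- Control: 280 low-risk men, 84 choose AS, 60 kept. The 316 active men fall 63.2 per cell, so 300 are kept, of whom 196/316 x 300 = 186 are low-risk.
- Intervention: 126 choose AS, 60 kept. The 274 active men fall 54.8 per cell, so all are kept, of whom 154 are low-risk.
- AS rate in followed low-risk men: 60/246 = 24.4% v 60/214 = 28.0%, a contrast of 3.7 points instead of 15.
- Low-risk share of followed men: 246/360 = 68.4% v 214/334 = 64.1%, where full follow-up gives 70% in both arms in expectation.

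**4. All scenarios by simulation** (20,000 trials each, pooled two-proportion z-test, two-sided 0.05; equal split / UPHS mix):

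| Low-risk | AS rates | Contrast in followed men (points) | Power, followed | Power, all men |
|---|---|---|---|---|
| 30% | 20 v 35 | 15.3 / 15.5 | 67 / 68% | 74% |
| 30% | 30 v 45 | 14.2 / 14.5 | 57 / 59% | 67% |
| 50% | 20 v 35 | 10.9 / 11.3 | 66 / 68% | 92% |
| 50% | 30 v 45 | 5.1 / 5.3 | 5 / 6% | 88% |
| 70% | 20 v 35 | 3.8 / 4.1 | 6 / 7% | 98% |
| 70% | 30 v 45 | 3.5 / 3.5 | 0.2 / 0.1% | 96% |

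The low-risk share (intervention minus control) differs by +0.4 to -4.3 points. With no shift (30% in both arms) the contrast is within 0.2 points of zero and the test rejects in 0-4% of trials. Between 95 and 145 men in total are over quota. With six equal treatment shares the figure is 89.

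**5. HRQoL.** Suppose AS and actively treated men differ by 7 points. The Accrual section calls that difference meaningful on SF sub-scales; using it as the AS-active gap is an assumption. The part of the arm difference that runs through AS choice is 7 x the arm difference in overall AS share. That share differs by 4.5 to 10.5 points in all men (0.31 to 0.74 HRQoL points) and by 1.0 to 5.3 points in followed men (0.07 to 0.37). The change runs from +0.04 to -0.66 points and is near zero at 30% low-risk. It scales with the assumed gap.

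**6. If every cell is filled, as D.2.1.2 literally says.** The overall AS share is then 60/360 in both arms by construction, whatever the true effect. Filling all 12 cells from 800 men is unlikely (probability about 5.5% even with equal shares), so enrolment would have to go on. If the rarest treatment had a 10% share, it would take 60/0.10 = 600 per arm, or 1,200 men, of whom 480 would not be followed.

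**The case against.** The strongest objections concern size and remedy, not the contradiction.

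- **The simulation stops at 400 per arm, whereas the plan fills every cell.** This is correct: 800 is an expectation, not a ceiling. But under the literal rule the overall AS difference disappears altogether and more men go unfollowed, so the objection does not weaken the point.
- **The 800 may be an attrition allowance only.** It equals 720/0.9 and is introduced that way. The documents give no number of men lost to quotas, so the 89 to 145 above is conditional on 800 being randomised. This stands.
- **Treatment choice can be recovered for everyone.** D.2.4.2.1 obtains it by self-report and chart review, and a man's treatment must be known before he can be over quota. So the AS figures apply only if that outcome is analysed in followed men. This also stands. It does not help the survey outcomes.
- **The HRQoL change is modest.** It is below 1.2 points throughout and rests on assumed inputs. That is fair as a limit on the stated size.
- **Weighting could repair it.** Weighting followed men by randomised/followed within each arm-by-treatment cell restored the all-men HRQoL difference in these scenarios (for example 0.08 back to 0.74). That requires early and late enrollees within a cell to be exchangeable, which the simulation builds in and the trial cannot take for granted. The plan contains no such weighting.

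**Conclusion.** The concern holds. The quota rule conflicts with the intent-to-treat statement and with the promise of surveys for all participants, and no rule says how unfollowed men enter the Aim 3 analysis. This rests on the text alone.

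The bias in the arm comparison is conditional on the intervention shifting choice. If it does not, the caps thin both arms alike and mainly affect generalisability. The size depends on low-risk share, AS uptake, treatment mix and the outcome gap, none of which the documents fix. Across the assumed scenarios the effect runs from negligible to the loss of most of the AS contrast. Because survey outcomes not collected at the time cannot be recovered at analysis, this needs settling before Phase 2 follow-up starts.

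**What to change.** 1. Remove the treatment-cell quota as a condition for follow-up. Follow and analyse every randomised man in his assigned arm, keeping 60 per treatment per arm only as a planning number.
2. Fix the number randomised in advance, reconcile 720 with 800, and state once where the 10% loss is allowed for.
3. Analyse AS versus active treatment in all randomised low-risk men.
4. Keep the mixed model with intervention group and hospital as the Aim 3 analysis. Label arm comparisons within treatment received as exploratory and non-randomised.
5. Restate the 3.0-point figure as conditional on 60 men per cell, and give it across the stated SD range.

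**Cost.** Protocol and SAP wording, plus follow-up payments of 4 x $20 = $80 per additional man. If 800 are randomised, that is 89 x $80 = $7,120 to 145 x $80 = $11,600. Survey, telephone and chart work is extra and not costed here, although the surveys are already promised to everyone. Fixing the number randomised also ends the open-ended filling of cells. The real downside is unequal cells, some below 60, so comparisons within and between treatments become less precise. The main HRQoL comparison loses nothing.
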